6.0 Complaints

A Complaint is any written, electronic, or oral communication that alleges deficiencies related to the physical characteristics, identity, quality, purity, potency, durability, reliability, safety, effectiveness, or performance of a product/device after it is released for distribution.

Complaints associated with any component of this investigational product must be reported to the Sponsor (Section 6.2.2). For adverse events, please refer to Sections 6.1 through 6.1.7. For product complaints, please refer to Section 6.2.

6.1 Medical Complaints

The investigator will monitor each subject for clinical and laboratory evidence of adverse events on a routine basis throughout the study. The investigator will assess and record any adverse event in detail including the date of onset, event diagnosis (if known) or sign/symptom, severity, time course (end date, ongoing, intermittent), relationship of the adverse event to study drug, and any action(s) taken. For serious adverse events considered as having "no reasonable possibility" of being associated with study drug, the investigator will provide another cause of the event. For adverse events to be considered intermittent, the events must be of similar nature and severity. Adverse events, whether in response to a query, observed by site personnel, or reported spontaneously by the subject will be recorded.

All adverse events will be followed to a satisfactory conclusion.

6.1.1 Definitions

6.1.1.1 Adverse Event

An adverse event (AE) is defined as any untoward medical occurrence in a patient or clinical investigation subject administered a pharmaceutical product and which does not necessarily have a causal relationship with this treatment. An adverse event can therefore be any unfavorable and unintended sign (including an abnormal laboratory finding),

symptom, or disease temporally associated with the use of a medicinal (investigational) product, whether or not the event is considered causally related to the use of the product.

Such an event can result from use of the drug as stipulated in the protocol or labeling, as well as from accidental or intentional overdose, drug abuse, or drug withdrawal. Any worsening of a pre-existing condition or illness including UC is considered an adverse event. Worsening in severity of a reported adverse event should be reported as a new adverse event. Laboratory abnormalities and changes in vital signs are considered to be adverse events only if they result in discontinuation from the study, necessitate therapeutic medical intervention, [meets protocol specific criteria see Section 6.1.7 regarding toxicity management)] and/or if the investigator considers them to be adverse events.

An elective surgery/procedure scheduled to occur during a study will not be considered an adverse event if the surgery/procedure is being performed for a pre-existing condition and the surgery/procedure has been pre-planned prior to study entry. However, if the pre-existing condition deteriorates unexpectedly during the study (e.g., surgery performed earlier than planned), then the deterioration of the condition for which the elective surgery/procedure is being done will be considered an adverse event.

6.1.1.2 Serious Adverse Events

If an adverse event meets any of the following criteria, it is to be reported to AbbVie as a serious adverse event (SAE) within 24 hours of the site being made aware of the serious adverse event.

Table 4. Serious Adverse Events

Death of Subject	An event that results in the death of a subject.
Life-Threatening	An event that, in the opinion of the investigator, would have resulted in immediate fatality if medical intervention had not been taken. This does not include an event that would have been fatal if it had occurred in a more severe form.
Hospitalization or Prolongation of Hospitalization	An event that results in an admission to the hospital for any length of time or prolongs the subject's hospital stay. This does not include an emergency room visit or admission to an outpatient facility.
Congenital Anomaly	An anomaly detected at or after birth, or any anomaly that results in fetal loss.
Persistent or Significant Disability/Incapacity	An event that results in a condition that substantially interferes with the activities of daily living of a study subject. Disability is not intended to include experiences of relatively minor medical significance such as headache, nausea, vomiting, diarrhea, influenza, and accidental trauma (e.g., sprained ankle).
Important Medical Event Requiring Medical or Surgical Intervention to Prevent Serious Outcome	An important medical event that may not be immediately life-threatening or result in death or hospitalization but based on medical judgment may jeopardize the subject and may require medical or surgical intervention to prevent any of the outcomes listed above (i.e., death of subject, life-threatening, hospitalization, prolongation of hospitalization, congenital anomaly, or persistent or significant disability/incapacity). Additionally, any elective or spontaneous abortion or stillbirth is considered an important medical event. Examples of such events include allergic bronchospasm requiring intensive treatment in an emergency room or at home, blood dyscrasias or convulsions that do not result in inpatient hospitalization, or the development of drug dependency or drug abuse.

For serious adverse events with the outcome of death, the date and cause of death will be recorded on the appropriate case report form.

6.1.1.3 Adverse Events of Special Interest

The following AEs of special interest will be monitored during the study (see detailed toxicity management in Section 6.1.7):

- Serious infections,
- opportunistic infections,
- herpes zoster,
- Active TB;
- Malignancy (all types);
- Adjudicated gastrointestinal perforations;
- Adjudicated cardiovascular events (e.g., major adverse cardiovascular event [MACE]);
- Anemia;
- Neutropenia;
- Lymphopenia;
- Renal dysfunction;
- Hepatic disorders;
- Elevated creatine phosphokinase (CPK);
- Adjudicated embolic and thrombotic events (non-cardiac, non-central nervous system [CNS]).

6.1.2 Adverse Event Severity

When criteria are available, events should be graded as described in the National Cancer Institute (NCI) Common Terminology Criteria for Adverse Events (CTCAE²⁶) version 4.03, which can be accessed at:

http://ctep.cancer.gov/protocolDevelopment/electronic_applications/ctc.htm#ctc_40.

If no grading criteria are provided for the reported event, then the event should be graded as mild, moderate, or severe per the investigator's judgment.

Mild (Grade 1)	Asymptomatic or mild symptoms; clinical or diagnostic observations only; intervention not indicated.
Moderate (Grade 2)	Minimal, local or noninvasive intervention indicated; limiting age-appropriate instrumental activities of daily living (ADL) (instrumental ADL refers to preparing meals, shopping for groceries or clothes, using the telephone, managing money, etc.).
Severe (Grade 3 - 5)	
Grade 3	Severe or medically significant but not immediately life-threatening; hospitalization or prolongation of hospitalization indicated; disabling; limiting self-care ADL (self-care ADL refers to bathing, dressing and undressing, feeding self, using the toilet, taking medications, and not bedridden).
Grade 4	Life-threatening consequences; urgent intervention indicated.
Grade 5	Death related to AE.

6.1.3 Relationship to Study Drug

The investigator will use the following definitions to assess the relationship of the adverse event to the use of study drug:

Reasonable Possibility	An adverse event where there is evidence to suggest a causal relationship between the study drug and the adverse event.
No Reasonable Possibility	An adverse event where there is no evidence to suggest a causal relationship between the study drug and the adverse event.

For causality assessments, events assessed as having a reasonable possibility of being related to the study drug will be considered "associated." Events assessed as having no reasonable possibility of being related to study drug will be considered "not associated." In addition, when the investigator has not reported causality or deemed it not assessable, AbbVie will consider the event associated.

[figure not shown]
If an investigator's opinion of no reasonable possibility of being related to study drug is given, another cause of event must be provided by the investigator for the serious adverse event.

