8.1.8.2 Analysis of Adverse Events

8.1.8.2.1 Treatment-Emergent Adverse Events

Adverse events (AEs) will be coded using the Medical Dictionary for Regulatory Activities (MedDRA) dictionary. Treatment-emergent adverse events, defined as AEs that began or worsened in severity after initiation of study drug in each period of the study, will be tabulated by system organ class (SOC) and MedDRA preferred term for each treatment group.

Adverse events starting more than 30 days following discontinuation of study drug will not be included in summaries of treatment-emergent AEs. When summarizing adverse events by relationship or severity, if a subject has an event with unknown severity or relationship then the subject will be counted in the severity/relationship category of "unknown" even if the subject has a second occurrence of the same event with a severity/relationship present. The only exception is if the subject has a second occurrence of the same event with the most extreme severity (i.e., "severe") or a relationship categories of "reasonable possibility." In this case, the subject will be counted under these most extreme severity/relationship categories.

Subjects reporting more than one AE for a given MedDRA preferred term will be counted only once for that term using the most severe incident in each study period. Subjects

reporting more than one type of event within an SOC will be counted only once for that SOC.

Frequencies and percentages of subjects with treatment-emergent AEs will be summarized for each treatment group as follows:

- Any event
- By system organ class, and preferred term
- By system organ class, preferred term and maximum relationship
- By system organ class, preferred term and maximum severity
- Any event and by system organ class and preferred term for events resulting in death
- Any event and by system organ class and preferred term for events resulting in study drug discontinuation
- Any event and by system organ class and preferred term for serious events
- Any event and by system organ class and preferred term for adverse events with a relationship of "reasonable possibility"
- Any event and by system organ class and preferred term for adverse events of special interest (serious infection, opportunistic infection, gastrointestinal perforations, malignancies, cardiovascular events [adjudicated events], drug-related hepatic disorders, increased serum creatinine and renal dysfunction, and increased CPK)

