9.2.2 Adverse Event Overview

An overview of AEs will be presented consisting of the number and percentage of subjects experiencing at least one event for each of the following AE categories:

- Any TEAE
- Any TEAE related to study drug according to the investigator
- Any severe TEAE
- Any serious TEAE
- Any TEAE leading to discontinuation of study drug
- Any TEAE leading to death
- TEAEs of Special Interest (as defined in [Appendix B](#))
- All deaths

- Deaths occurring \leq 30 days after last dose of study drug
- Deaths occurring $>$ 30 days after last dose of study drug

In addition, an overview of AEs per 100 patient-years of study exposure will be presented for the AE categories defined above. The number of TEAEs reported, the total number of years of study drug exposure, and the TEAE rate per 100 patient-years will be presented. For the SA_A and SA_C populations, 95% CI will be provided for the treatment differences between each upadacitinib group and placebo group. The treatment difference and 95% CI will be adjusted by the study size of the Phase 2b Induction Study and Induction Studies described by Sui et al.⁷

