9.2.3 Treatment-Emergent Adverse Events by SOC and/or PT

Treatment-emergent adverse events will be summarized by SOC and PT; by maximum relationship to study drug as assessed by the investigator (e.g., reasonable possibility or no reasonable possibility) and SOC and PT; by maximum severity and SOC and PT; and by subject number and SOC and PT. Specific adverse events will be counted once for each subject for calculating percentages, unless stated otherwise. In addition, if the same adverse event occurs multiple times within a subject, the highest severity and level of relationship to investigational product will be reported. The SOCs will be presented in alphabetical order, and the PTs will be presented in alphabetical order within each SOC.

For summary by maximum severity, if a subject has an AE with an unknown severity, then the subject will be counted in the severity category of unknown, even if the subject has another occurrence of the same event with a severity present. The only exception is if the subject has another occurrence of the same AE with the most extreme severity – severe. In this case, the subject will be counted under the severe category.

For summary by maximum relationship to study drug, if a subject has an AE with an unknown relationship, then the subject will be counted in the relationship category of "unknown," even if the subject has another occurrence of the same event with a relationship present. The only exception is if the subject has another occurrence of the

same AE with a relationship assessment of "Reasonable Possibility." In this case, the subject will be counted under the "Reasonable Possibility" category.

In addition, treatment-emergent adverse events will be summarized by PT and sorted by decreasing frequency for the upadacitinib overall.

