In treatment-emergent AE tables, a subject who reports more than one treatment-emergent AE in different system organ classes will be counted only once in the overall total. A subject who reports two or more different preferred terms which are in the same SOC will be counted only once in the SOC total. A subject who reports more than one treatment AE with the same preferred term will be counted only once for that preferred term using the most extreme incident (i.e., most "severe" for the severity tables and most "related" for the relationship tables).

Adverse events will also be summarized by maximum severity. If a subject has an adverse event with unknown severity, then the subject will be counted in the severity category of "unknown," even if the subject has another occurrence of the same adverse event with a severity present. The only exception is if the subject has another occurrence of the same adverse event with the most extreme severity – "Severe." In this case, the subject will be counted under the "Severe" category.

Adverse events will also be summarized by maximum relationship to study, as assessed by the investigator. If a subject has an adverse event with unknown relationship, then the subject will be counted in the relationship category of "unknown," even if the subject has another occurrence of the same adverse event with a relationship present. The only exception is if the subject has another occurrence of the same adverse event with a relationship assessment of "Reasonable Possibility." In this case, the subject will be counted under the "Reasonable Possibility" category, respectively.

Incidence rates per 100 patient years of exposure to study drug will be presented for AE overviews and for AEs by SOC and preferred term where the number of events will be used as the numerator.

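### Events with missing or unassessable causality are associated with study drug under Protocol 6.1.3, but are 'unknown' in the relationship summaries and fall outside the related-TEAE outputs

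*Protocol*

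**What the plan says.** **Causality rule.** Protocol 6.1.3 gives the investigator two ratings, reasonable possibility and no reasonable possibility, and maps them to associated and not associated. It then closes the gap for unrated events: "when the investigator has not reported causality or deemed it not assessable, AbbVie will consider the event associated". Nothing in that section limits the default to expedited reporting.

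**Analysis rule in the protocol.** For summaries by relationship or severity, Protocol 8.1.8.2.1 says that "if a subject has an event with unknown severity or relationship then the subject will be counted in the severity/relationship category of" 'unknown'. This holds even if the same event occurred a second time with a rating. The one exception for relationship is a second occurrence rated 'reasonable possibility'. The same section plans a table restricted to events with that rating.

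**Analysis rule in the SAPs.** Section 9.2.3 of the Substudy 3 SAP says, for the maximum-relationship summary, that "if a subject has an AE with an unknown relationship, then the subject will be counted in the relationship category of" 'unknown', with the same exception. Section 9.2.3 of the Substudy 2 SAP repeats this. Section 11.2.1 of the Substudy 1 SAP has the equivalent: "If a subject has an adverse event with unknown relationship, then the subject will be counted in the relationship category of" 'unknown'.

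**Related-event row.** The adverse event overview in section 9.2.2 of the Substudy 2 and 3 SAPs has a row for "Any TEAE related to study drug according to the investigator". The Substudy 1 overview (11.2.1) uses the investigator's reasonable-possibility rating.

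**The concern.** Under 6.1.3 every event ends up either associated or not associated. The analysis text brings back a third class that 6.1.3 had removed, and the related-event outputs leave that class out. The same event is then associated in one section of the protocol and absent from the related-event table in another. No SAP applies the 6.1.3 default. Neither the version histories of the Substudy 2 and 3 SAPs nor the change summary of the Substudy 1 SAP says that it was set aside.

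At stake is the related-TEAE figure reported for each arm, as a number and percentage of subjects and as a rate per 100 patient-years. In Substudy 3, section 9.2.2 also provides 95% CIs for the differences from placebo in the SA_A and SA_C populations.

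The plan handles another kind of missing adverse event data cautiously: under section 9.2.1 of the Substudy 2 and 3 SAPs, an event with an incomplete onset date is taken as treatment-emergent unless other evidence shows that it was not. Missing causality has a cautious default in the protocol too, but the tables do not use it.

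**Working it through.** The plan gives no figure to reproduce. The check follows one event through the rules and then bounds the effect.

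**1. One TEAE with causality missing or judged not assessable, and no other occurrence of it rated 'reasonable possibility'**

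| Place | Where the event goes |
|---|---|
| Protocol 6.1.3 | Associated, the same class as reasonable possibility |
| Protocol 8.1.8.2.1, summary by relationship | Unknown |
| Protocol 8.1.8.2.1, reasonable-possibility table | Not included |
| Substudy 2 and 3 SAPs, 9.2.3, maximum relationship | Unknown |
| Substudy 2 and 3 SAPs, 9.2.2, related row | Not included, because the investigator did not rate it as related |
| Substudy 1 SAP, 11.2.1 | Unknown in the maximum-relationship summary; not included in the related row |

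Two steps are inferences. The first is that 'unknown' covers both unreported and not-assessable causality; no document defines it. The second is that the event leaves the related row; this follows from the row's definition, and no sentence states it.

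**2. Direction within an arm.** Let A be the subjects with at least one TEAE rated 'reasonable possibility', and M the subjects with at least one TEAE of missing or unassessable causality.

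- Related row as planned: |A|
- Related row under 6.1.3: |A ∪ M| = |A| + |M not in A|
- Shortfall: |M not in A|, which is zero or more

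Subjects in both sets are already in the row, so only subjects with no investigator-related TEAE are lost from the subject count. The rates per 100 patient-years count events (Substudy 3 SAP 9.2.4), so there a missing-causality event is lost even if the subject has another related event. The exception is the same preferred term on the same day, which is counted once.

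**3. Size.** The frequency of missing causality is not in the documents. Let p be the assumed proportion of an arm in M but not in A, with n = 150 per arm (Substudy 3 SAP 2.4). The shortfall is n × p subjects, or p as a percentage of the arm.

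| Assumed p | Shortfall, subjects per arm | Shortfall, percentage points |
|---|---|---|
| 0% | 150 × 0 = 0 | 0 |
| 1% | 150 × 0.01 = 1.5 | 1 |
| 2% | 150 × 0.02 = 3 | 2 |
| 5% | 150 × 0.05 = 7.5 | 5 |

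**4. Between-arm difference.** With equal arms of size n, applying 6.1.3 shifts the difference from placebo by (m_U − m_P)/n, where m_U and m_P are the shortfalls on upadacitinib and placebo. If m_U = 3 and m_P = 1, the shift is 2/150 = +1.3 points. If m_U = 1 and m_P = 3, it is −1.3 points. The documents do not fix the sign.

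**The case against.** The strongest defence is that the two rules describe different things. Section 6.1.3 says how the sponsor regards an event and sits with adverse event assessment and reporting, not in Section 8. The tables report the investigator's opinion and are labelled that way, and an event that the investigator did not rate is not related according to the investigator. Section 8 has its own rule for tabulation, and the SAPs follow it. On this reading both rules can be obeyed at once.

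That reading is plausible, but the documents never state it, and 6.1.3 carries no restriction to reporting. The part that stands is that the SAPs do not depart from Protocol 8.1.8.2.1. The inconsistency is inside the protocol, so the repair has to start there.

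A second point also stands: the events are not concealed. They appear as 'unknown', a category that takes precedence over 'no reasonable possibility', and all TEAEs and all SAEs are tabulated whatever their causality.

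Three stronger readings are tempting, and the documents support none of them:

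- *Drug-related events are in fact undercounted.* This needs some events with missing causality, and no frequency is given.
- *The Substudy 3 CI for the difference from placebo errs low.* Causality can be missing in any arm and assessment is double-blind, so step 4 applies and the sign is open.
- *Related serious events would be heavily understated.* No overview or table list contains a related-serious row. Related and serious are separate rows, and no counts are given from which to work out a relative effect.

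**Conclusion.** The inconsistency is real and appears in the protocol and all three SAPs. The firm conclusion is one-sided and limited: in each arm, the related-TEAE count as planned is at most the count under the protocol's own causality rule. It rests on the two inferences in step 1. The amount is unknown, may be zero, and on the assumed range of 1% to 2% would be 1.5 to 3 subjects in an arm of 150. No efficacy result is touched. It is a minor point, worth correcting because the correction is cheap and could change a reported safety figure.

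**What to change.** **Substudies 2 and 3.** In Protocol 8.1.8.2.1 and in sections 9.2.2 and 9.2.3 of the two SAPs, count missing or not-assessable causality as related in three places: the related-TEAE overview row, the reasonable-possibility tables, and the maximum-relationship summary. Retitle the overview row, for example 'related per investigator, or causality missing or not assessable'; under its present title it would be mislabelled once sponsor-classified events were added. Footnote the number so classified in each arm, so that the investigator-only count can be recovered. The 'unknown' rule for severity stays as it is.

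**Substudy 1.** The dose-selection analysis has already been done, so leave its tables alone and add only a footnoted supplementary count under the 6.1.3 rule.

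**Minimum alternative.** If the sponsor means the tables to show investigator opinion only, say so in Protocol 8.1.8.2.1 and the SAPs, and add one summary under the 6.1.3 default.

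**Cost.** One mapping rule in the programs, a row title, a footnote, and matching text in the protocol and two SAPs, plus the supplementary count for Substudy 1. No new data are needed. Related-TEAE rates may rise slightly in any arm, including placebo.
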